#### **Kinetics of ADA response**

Kinetics of ADA response will be derived for participants with treatment-induced/boosted ADA considering ADA samples collected during the TE period and post-treatment period.

- **Time to onset of ADA response** is defined as the time period between the first IMP administration and the first treatment-induced/boosted ADA.

[figure not shown]
- **Duration of ADA response** is defined as the time between the first treatment-induced/boosted ADA and the last treatment-induced/boosted ADA, irrespective of negative samples or positive samples not reaching the boosted threshold in-between. ADA duration will be summarized only for participants with persistent ADA response.
  - A positive sample (boosted positive sample for participants with pre-existing ADA) occurring after the TE period will be considered as treatment-induced/boosted ADA if a previous treatment-induced/boosted ADA occurred during the TE period and less than 16 weeks before this sample
- **Persistent ADA response** is defined by treatment-induced/boosted ADA with a duration of ADA response of at least 16 weeks.
- **Transient ADA response** is defined by treatment-induced/boosted ADA with a duration of ADA response of less than 16 weeks and the last sample of the TE period is not treatment-induced/boosted.
- **Indeterminate ADA response** is defined by treatment-induced/boosted ADA that are neither persistent nor transient.

**ADA response variable:**

- **ADA incidence** is defined as the proportion of participants found to have seroconverted (treatment-induced ADAs) or boosted their pre-existing ADA response (treatment-boosted ADAs) at any time point during the TE period.
- **Incidence of ADAs** directed against PEG moiety of SAR444245 is defined as the proportion of participants with ADAs directed against PEG moiety of SAR444245 during the TE period among evaluable participants. Participants from ADA population are evaluable for ADAs directed against PEG moiety except if ADAs directed against PEG moiety status is not determined on an ADA against SAR444245 positive sample
- **Incidence of ADAs cross-reacting with endogenous IL-2** is defined as the proportion of participants with ADAs directed against endogenous IL-2 during the TE period among evaluable participants. Participants from ADA population are evaluable for ADAs directed against endogenous IL-2 except if their status is not determined on an ADA against SAR444245 positive sample.

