## 1.2 OBJECTIVE AND ENDPOINTS

**Table 2 - Objectives and endpoints - master protocol**

Objectives	Endpoints
Primary	

 
To determine the antitumor activity of SAR444245 in combination with other anticancer therapies
 
	
 
Objective response rate (ORR) defined as the proportion of participants who have a confirmed complete response (CR) or partial response (PR) determined by Investigator per Response Evaluation Criteria in Solid Tumors (RECIST) 1.1
 

Secondary	

 
To assess the safety of SAR444245 in combination with other anticancer therapies
 
To assess other indicators of antitumor activity
 
	
 
Incidence of treatment emergent adverse events (TEAEs), serious adverse events (SAEs), laboratory abnormalities according to National Cancer Institute Common Terminology Criteria for Adverse Events (NCI CTCAE) V5.0 and American Society for Transplantation and Cellular Therapy (ASTCT) consensus grading
 
Time to response (TTR) defined as the time from the first administration of investigational medicinal product (IMP) to the first tumor assessment at which the overall response was recorded as PR or CR that is subsequently confirmed and determined by Investigator per RECIST 1.1
 
Duration of response (DoR), defined as the time from first documented at which the overall response was recorded as CR or PR that is subsequently confirmed until documented progressive disease (PD) determined by Investigator per RECIST 1.1 or death from any cause, whichever occurs first
 
Clinical benefit rate (CBR) including confirmed CR or PR at any time or stable disease (SD) of at least 6 months determined by Investigator per RECIST 1.1.
 
Progression-free survival (PFS), defined as the time from the date of first IMP administration to the date of the first documented disease progression determined by Investigator as per RECIST 1.1 or death due to any cause, whichever occurs first
 
Plasma concentrations and where applicable PK parameters of SAR444245
 
Incidence of anti-drug antibodies (ADAs) against SAR444245
 

Exploratory	     

Objectives	Endpoints
[REDACTED]	[REDACTED]

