**Table 5 - Populations for analyses**

Population	Description
Screened	All participants who have given their informed consent.
Enrolled	All participants who have given their informed consent and have been allocated to an intervention (by IRT) regardless of whether the intervention was received or not.
Exposed	All participants who have given their informed consent and received at least one dose (even incomplete) of IMP (SAR444245 or other anticancer therapies).
Population without trial impact (disruption) due to COVID-19	All exposed participants: 

without any critical or major deviation related to COVID-19

and who did not permanently discontinue treatment due to COVID-19

and who did not permanently discontinue study due to COVID-19

Efficacy	All participants from the exposed population with at least one evaluable post-baseline tumor assessment or who permanently discontinued study treatment.
Response-evaluable	All participants from efficacy population with an evaluable baseline and at least one evaluable post-baseline tumor assessments. Participants who died from disease progression before any TA will also be response-evaluable.
Pharmacokinetic (PK)	All participants from exposed population with at least 1 PK concentration available after the first dose of study intervention.
ADA	All participants from exposed population with at least 1 ADA result (positive, negative or inconclusive) after the first dose of study intervention.
Pharmacodynamics (PDy)	All participants from the exposed population with at least 1 PDy parameter assessed after the first dose of study intervention.

Participants exposed to study intervention before or without being enrolled will not be considered enrolled and will not be included in any analysis population. The safety experience of these participants will be reported separately.

For any participant enrolled and treated more than once, only the data associated with the first enrollment will be used in any analysis population. The safety experience associated with any later enrollment will be reported separately

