#### 3.7.1.2 Immunogenicity analyses

Participant's ADA status, response variable and kinetics of ADA responses (see definitions below) will be summarized on the ADA population.

Kinetics of ADA responses will be described for participants with treatment-induced ADA and for participants with treatment-boosted ADA, separately. Time to ADA onset and duration of ADA will be described with minimum, Q1, median, Q3 and maximum statistics.

Peak titer will be described with minimum, Q1, median, Q3 and maximum statistics for participants with treatment-induced ADA and for participants with treatment-boosted ADA, separately.

ADAs against SAR444245 (negative, positive, inconclusive) and corresponding titers, ADAs directed against PEG moiety of SAR444245 status (negative, positive) and ADAs cross-reacting with endogenous IL-2 status (negative, positive) will also be described overtime using descriptive statistics. ADAs directed against PEG moiety of SAR444245 status and ADAs cross-reacting with endogenous IL-2 status will only be determined if the status of ADAs against SAR444245 is positive.

The impact of positive immune response on efficacy, PK and safety variables may be further explored, depending on ADA incidence.

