#### **Participant's ADA status against SAR444245**

- Participants with **pre-existing ADAs** correspond to participants with ADAs present in samples drawn before first administration of intervention. Participants with missing ADA sample at baseline will be considered as without pre-existing ADA.
- Participants with **treatment-emergent ADA** correspond to participants with at least one treatment-induced/boosted ADA.
  - Participants with **treatment-induced ADAs** correspond to participants with ADAs that developed during the treatment-emergent (TE) period and without pre-existing ADA (including participants without pre-treatment samples).
  - Participants with **treatment-boosted ADAs** correspond to participants with pre-existing ADAs that are boosted during the TE period to a significant higher titer than the baseline. A 2-fold serial dilution schema is used during titration, so at least a 4-fold increase will be considered as significant.
- Participants with **unclassified ADA** correspond to participants with pre-existing ADAs that cannot be classified as treatment-boosted ADA because of missing titer(s) (ie, a positive ADA sample during the TE period in a participant with pre-existing ADA but with missing titer at this sample or at baseline).
- Participants **without treatment-emergent ADA** correspond to participants without treatment-induced/boosted ADA and without any inconclusive sample nor unclassified ADA during the TE period.
- Participants **with inconclusive ADA** are defined as participants which cannot irrefutably be classified as with or without treatment-emergent ADA.

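### ADA incidence has no evaluability condition, so participants with only inconclusive results or with unclassified ADA count as non-cases and the reported figure is only a lower bound

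*SAP*

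**What the plan says.** SAP Table 2 lists "Incidence of anti-drug antibodies (ADAs) against SAR444245" as a secondary endpoint. Four parts of the SAP fix how it is calculated.

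- **Denominator.** Section 3.7.1.2 states: "Participant's ADA status, response variable and kinetics of ADA responses (see definitions below) will be summarized on the ADA population". The response variable includes ADA incidence.
- **Entry to that population.** Table 5 requires "at least 1 ADA result (positive, negative or inconclusive) after the first dose of study intervention". An inconclusive result alone is enough.
- **Numerator.** Under the ADA response variable, incidence "is defined as the proportion of participants found to have seroconverted (treatment-induced ADAs) or boosted their pre-existing ADA response". The definition carries no evaluability condition.
- **Participant classes.** Participants without treatment-emergent ADA must be "without any inconclusive sample nor unclassified ADA during the TE period". Inconclusive participants "are defined as participants which cannot irrefutably be classified as with or without treatment-emergent ADA". A separate unclassified group holds participants with pre-existing ADA and a positive TE-period sample whose titer, or baseline titer, is missing.

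The anti-PEG and IL-2 cross-reacting incidences are restricted to evaluable participants. The anti-PEG rule begins "Participants from ADA population are evaluable for ADAs directed against PEG moiety except if", and the only exception is an undetermined status on a sample positive for ADA against SAR444245. The IL-2 rule is parallel. Section 3.7.1.2 also says that both statuses are determined only when the main ADA result is positive.

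**The concern.** The participant classes separate people known to be without treatment-emergent ADA from people whose status is unknown. The incidence formula does not keep that separation: the unknown group stays in the denominator and cannot reach the numerator. For a given true frequency, the reported incidence can therefore fall as more assay results are inconclusive or more titers are missing.

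The next two definitions in the same list do restrict the denominator, so the missing condition on the main endpoint looks like an omission. Elsewhere the SAP resolves unknowns against the drug: section 3.6.2 treats a missing causal relationship as related, and section 3.2.2 treats a missing response as non-response. Here an unknown lowers the reported immunogenicity, and the SAP does not say that this is intended.

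At stake is the reading of one descriptive secondary endpoint and of two related incidences.

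**Working it through.** The SAP states no ADA incidence and no rate of inconclusive results, so there is no figure of its own to reproduce.

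**Inputs**
- N = 40, taken from the approximate cohort size in section 4. The ADA population could be smaller.
- K = number with treatment-induced or treatment-boosted ADA. Assumed: 8, with 4 and 20 as alternatives.
- m = number classed as inconclusive or unclassified. Assumed: 1 to 8.

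**Formulas**
- Incidence as the SAP defines it: K/N.
- Lower bound, if none of the m is truly positive: K/N.
- Upper bound, if all m are truly positive: (K+m)/N.
- Incidence with all m removed, for comparison only: K/(N−m).

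**Results for K=8, N=40**

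| m (assumed) | SAP figure K/N | Upper bound (K+m)/N | K/(N−m) |
|---|---|---|---|
| 1 | 8/40 = 20.0% | 9/40 = 22.5% | 8/39 = 20.5% |
| 2 | 20.0% | 10/40 = 25.0% | 8/38 = 21.1% |
| 4 | 20.0% | 12/40 = 30.0% | 8/36 = 22.2% |
| 8 | 20.0% | 16/40 = 40.0% | 8/32 = 25.0% |

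With m=4, K=4 gives a range of 10.0% to 20.0%, and K=20 gives 50.0% to 60.0%. The width is always m/N. The SAP figure is always the lower end, so this feature can understate incidence but cannot overstate it.

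**Why not remove all m.** One inconclusive TE-period sample takes a participant out of the class without treatment-emergent ADA, even if every other sample is negative. One treatment-induced or boosted sample makes a participant a case whatever the other samples show. Removing the whole inconclusive class therefore removes only non-cases. Suppose four participants each have one inconclusive sample among conclusive negatives and are truly negative. K/N = 8/40 = 20.0% is then correct, and 8/36 = 22.2% is too high.

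**A narrower exclusion.** Let e (at most m) be the participants whose TE-period samples are all inconclusive, plus the unclassified. With m=4 and an assumed e=2, the main figure is 8/(40−2) = 8/38 = 21.1%, reported beside bounds of 20.0% to 30.0%.

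**Anti-PEG and IL-2.** A participant whose main-assay samples are all inconclusive has no positive sample, so neither status is ever determined. The exception to evaluability applies only to positive samples, so this participant stays evaluable and counts as a non-case. Unclassified participants do have a positive sample and fall under the existing rule, so they need no further exclusion here.

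**The case against.** The strongest reply is that nothing is hidden. The SAP gives inconclusive and unclassified participants their own classes and summarizes ADA status on the same population, so a reader can find m and work out the bounds. All ADA output is descriptive. No stopping rule or primary endpoint uses it, and further exploration of ADA impact is optional with no threshold. For K=8 even the 5-point difference between K/N and K/(N−m) at m=8 lies inside the 90% interval for 8/40 in Table 14 (10.4% to 33.2%). All of this stands, and it limits the severity.

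Three stronger readings are tempting, and the SAP does not support them:

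- *That the incidence conflicts with the participant-status summary.* Treatment-emergent ADA in that summary is induced plus boosted, on the same population, so both give K/N.
- *That the SAP classes these participants as ADA-negative.* It expressly does not. They act as non-cases only in the incidence arithmetic.
- *That K/(N−m) is the true incidence and its gap from K/N is the bias.* That holds only if undetermined participants are positive as often as the rest, for which the SAP gives no basis. If most are truly negative, K/N is nearer the truth.

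What the reply does not answer is that the endpoint figure itself is a lower bound presented as an estimate, or that the anti-PEG and IL-2 rule calls untested participants evaluable.

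**Conclusion.** The point holds as a gap in the denominator definition, of minor to moderate importance. ADA incidence as written is the lower end of K/N to (K+m)/N, and it equals the true proportion only if m is zero or every undetermined participant is truly negative. For N=40 the range is 2.5 points wide at m=1, 10 points at m=4 and 20 points at m=8. These values of m are assumptions; the actual size is unknown and small if inconclusive results and missing titers are rare. The anti-PEG and IL-2 incidences share the flaw for the narrower group with only inconclusive main-assay results, whose size is also unknown.

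**What to change.** Amend the ADA response variable definitions in section 3.7.1.2:

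1. Restrict all three incidences to evaluable participants. Exclude those whose TE-period main-assay samples are all inconclusive. For overall ADA incidence, also exclude those with unclassified ADA.
2. State that anyone with a treatment-induced or treatment-boosted sample remains a case, whatever the other samples show.
3. State that a participant with an inconclusive sample among conclusive negatives stays in the main denominator.
4. Report the number excluded from each incidence. For overall ADA incidence, also report the bounds K/N to (K+m)/N, with m counting all inconclusive or unclassified participants.

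This takes a few sentences and no new data. The participant classes are already defined; only a flag for all-inconclusive TE-period samples has to be added. The downside is a slightly smaller denominator and a slightly higher reported incidence.

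### Anti-PEG and IL-2 cross-reacting 'incidence' count any positive result in the treatment-emergent period, whereas ADA incidence counts only induced or boosted antibodies

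*SAP*

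**What the plan says.** All three definitions stand together in SAP Section 3.7.1.2, under the ADA response variable.

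- **ADA incidence** covers participants "found to have seroconverted (treatment-induced ADAs) or boosted their pre-existing ADA response (treatment-boosted ADAs) at any time point during the TE period".
- **Anti-PEG incidence** is "the proportion of participants with ADAs directed against PEG moiety of SAR444245 during the TE period among evaluable participants".
- **IL-2 cross-reacting incidence** is "the proportion of participants with ADAs directed against endogenous IL-2 during the TE period among evaluable participants".

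Evaluability for the anti-PEG measure is set as follows: "Participants from ADA population are evaluable for ADAs directed against PEG moiety except if ADAs directed against PEG moiety status is not determined" on an ADA-positive sample. The IL-2 rule is equivalent. Being positive at baseline does not remove anyone.

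Earlier in the same section, the two specificity statuses "will only be determined if the status of ADAs against SAR444245 is positive". They are reported as negative or positive. A titer is named only for ADA against SAR444245.

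The list of participant ADA statuses defines pre-existing ADA ("participants with ADAs present in samples drawn before first administration of intervention"), and also the induced, boosted and unclassified classes. All of these refer to ADA against SAR444245.

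**The concern.** Incidence normally means new cases, and the first of the three definitions uses it that way. The other two count any positive in a period. A participant who is anti-PEG positive before the first dose, and is still positive on treatment with no significant titer rise, is a case under the second definition and not under the first. So is a participant with pre-existing ADA that cannot be classified because a titer is missing, provided a TE sample is positive for the specificity.

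The three percentages are likely to be reported close together under one label. A reader will tend to take the specificity figures as a breakdown of the antibodies that emerged on treatment, which they are not. The distinction matters most for cross-reactivity with endogenous IL-2, where the question is whether the drug raised the antibody or the participant already had it.

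**Working it through.** The SAP states no figure for any of these measures, so there is nothing to reproduce. The check compares the definitions and then counts the same hypothetical participants under both rules.

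**Step 1. Does the TE period itself imply emergence?** No. SAP Section 3.1 defines it by dates only, from the first IMP administration to 30 days after the last. Where the SAP means emergence it adds a condition: no pre-existing ADA, or at least a 4-fold titer rise.

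**Step 2. Are the induced and boosted classes extended to PEG or IL-2?** No. They are defined only for ADA against SAR444245.

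**Step 3. Can an unboosted pre-existing antibody be tested and counted?** Yes. The precondition for specificity testing is a positive ADA sample, not an induced or boosted one. The pre-dose sample itself lies outside the TE period, so the antibody must still be detected on a TE sample.

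**Step 4. Size of the gap.** Among N evaluable participants, let

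- a = participants with induced or boosted ADA whose qualifying sample is positive for the specificity,
- u = participants positive for the specificity on a TE sample whose pre-existing ADA is unboosted,
- c = participants positive for the specificity on a TE sample whose ADA is unclassified for missing titers.

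SAP rule: (a + u + c)/N. Induced-or-boosted rule: a/N. Gap: (u + c)/N.

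**Step 5. Illustration.** N = 40 is the planned cohort size in SAP Section 4, with all participants assumed evaluable. All other counts are assumptions: a = 2 newly induced, c = 0, every baseline positive persists, none is boosted, and every ADA is PEG-positive.

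| Baseline positives (u) | SAP rule | Induced or boosted | Gap |
|---|---|---|---|
| 0 | 2/40 = 5% | 2/40 = 5% | 0 points |
| 2 | 4/40 = 10% | 5% | 5 points |
| 4 | 6/40 = 15% | 5% | 10 points |
| 8 | 10/40 = 25% | 5% | 20 points |
| 16 | 18/40 = 45% | 5% | 40 points |

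In the row with 8 baseline positives, ADA incidence is 2/40 = 5% and anti-PEG incidence is 25%.

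**Step 6. Weaker persistence.** Take 8 baseline positives, of whom 4 are still positive in the TE period and 1 of those 4 is boosted, plus 2 induced. The SAP rule gives (4 + 2)/40 = 15%. The induced-or-boosted rule gives (1 + 2)/40 = 7.5%. The gap falls to 7.5 points.

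**The case against.** The strongest reply is that the specificity definitions are transparent. They say what is counted, never call it induced, boosted or treatment-emergent, and sit beside a definition that does. The SAP also describes PEG and IL-2 status over time, so baseline positivity should be visible where it was tested. The endpoint in SAP Table 2 is incidence of ADA against SAR444245, whose definition is sound, and no decision rule uses the specificity figures. This makes the matter modest, but it does not remove it: the label is still shared by two different counts, and a description over time does not change either numerator.

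Four stronger readings are tempting and are not supported.

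- *A specificity incidence above ADA incidence is impossible because it is a subset.* The SAP makes PEG-positive participants a subset of ADA-positive participants, including those with pre-existing ADA, not of treatment-emergent ADA. The denominators can also differ, because the specificity measures drop participants with undetermined status.
- *The SAP reports pre-existing reactivity as caused by treatment.* It makes no causal statement. A reader might infer one from the word incidence.
- *Baseline specificity is always available.* A positive ADA is a necessary condition for testing, not a promise that every positive sample is tested. The evaluability rule provides for undetermined results.
- *The figures are overstated by a known amount.* The SAP gives no baseline prevalence. Any figure also rests on assumed persistence and boosting, as Step 6 of the working shows.

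**Conclusion.** The point holds as a mismatch of definitions. Followed as written, the SAP counts pre-existing antibodies that persist unboosted, and ADA that cannot be classified, as incident anti-PEG or IL-2 cross-reacting cases, while leaving the same participants out of ADA incidence. The two specificity figures can therefore exceed what emerged on treatment.

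The gap is (u + c)/N. It is nil if nobody is positive at baseline and 20 points in the assumed case of 8 persistent unboosted participants among 40. Its actual size cannot be known from the SAP. For unclassified participants the true status is unknown, so their part of the gap is a difference in counting rather than a demonstrated overstatement.

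ADA incidence is not a perfect benchmark either: participants with no baseline sample are treated as having no pre-existing ADA, so it may include some antibodies that predate treatment.

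The consequence is limited to descriptive immunogenicity tables. ORR and the futility rule are untouched. The definitions should be aligned before those tables are programmed.

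**What to change.** Revise the two specificity definitions in SAP Section 3.7.1.2.

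1. Numerator: evaluable participants with treatment-induced or treatment-boosted ADA against SAR444245 whose qualifying (induced or boosted) TE sample is positive for that specificity.
2. Do not exclude boosted participants who were already positive for the specificity at baseline. ADA incidence counts them, and the SAR444245 titer is the only one named for judging a boost.
3. Report participants positive for the specificity at baseline, where tested, on a separate pre-existing line.
4. If the any-positive count is kept, label it 'prevalence during the TE period'.

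With 8 persistent unboosted and 2 induced among 40, the table would show incidence 2/40 = 5%, pre-existing 8/40 = 20%, and, if kept, prevalence 10/40 = 25%.

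The cost is two edited definitions and one extra table line. There are two limits. Participants whose baseline specificity was not determined cannot be placed on the pre-existing line. A participant whose unboosted pre-existing ADA first becomes specificity-positive on treatment would not enter the incidence, and would appear only in the prevalence line and the description over time.

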## 4 SAMPLE SIZE DETERMINATION

As the study is not intended to explicitly test a hypothesis, calculations of power and Type I error were not considered in the study design.

The plan is to treat approximately 40 participants in each cohort.

**Table 14** lists estimated ORR and 90% exact confidence intervals (CIs) by number of responders from a sample size of 40 participants treated.

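### The evaluability rule for anti-PEG and IL-2 cross-reacting antibodies removes participants already shown positive when another ADA-positive sample lacks the result

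*SAP*

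**What the plan says.** SAP section 3.7.1.2, under the ADA response variable, defines two sub-specificity incidences. The anti-PEG incidence is the "proportion of participants with ADAs directed against PEG moiety of SAR444245 during the TE period among evaluable participants". The IL-2 incidence is the "proportion of participants with ADAs directed against endogenous IL-2 during the TE period among evaluable participants".

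Each bullet then says who is evaluable. For anti-PEG, members of the ADA population are evaluable "except if ADAs directed against PEG moiety status is not determined on an ADA against SAR444245 positive sample". For IL-2 they are evaluable "except if their status is not determined on an ADA against SAR444245 positive sample". The ADA population (Table 5) is made up of exposed participants with "at least 1 ADA result (positive, negative or inconclusive) after the first dose of study intervention".

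Two further statements in section 3.7.1.2 matter. The sub-specificity statuses "will only be determined if the status of ADAs against SAR444245 is positive", and they "will also be described overtime using descriptive statistics", so one participant can contribute several ADA-positive samples.

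**The concern.** Both rules turn on the indefinite article: one ADA-positive sample without a sub-specificity result is enough to make the participant non-evaluable. No exception is made for a participant whose status was determined as positive on another TE-period sample. That participant's answer to the incidence question is already known, and the rule discards it.

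The exclusion is also selective. Sub-specificity is tested only where ADA is positive, so a participant who is never ADA-positive cannot be excluded. Those with the most ADA-positive samples have the most chances of one missing result.

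The numerator is confined to the TE period, but the exclusion sentence states no window. An undetermined result on an ADA-positive baseline or post-treatment sample could therefore be read as removing a participant with a TE-period positive.

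The SAP ranks evidence differently elsewhere in the same section. Under the participant's ADA status, one treatment-induced or boosted result makes the participant treatment-emergent positive, and inconclusive or unclassified samples only prevent a negative classification. The two sub-specificity rules reverse that order.

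**Working it through.** The SAP gives no anti-PEG or IL-2 incidence and no undetermined rate, so there is no stated figure to reproduce. The inputs from the document are the two rules above and the cohort size: "The plan is to treat approximately 40 participants in each cohort". All other inputs below are assumptions.

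**Step 1: dropping known positives.** Let N be the otherwise evaluable participants, K the known positives among them, and m the known positives who also have an ADA-positive sample with undetermined status.

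- Known positives kept: K/N.
- Literal rule: (K-m)/(N-m).
- Difference: (K-m)/(N-m) - K/N = -m(N-K)/[N(N-m)], which is negative whenever m>0 and K<N.

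With N=40 and assumed K and m:

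- K=4, m=1: 3/39 = 7.7% against 4/40 = 10.0%.
- K=4, m=2: 2/38 = 5.3% against 10.0%.
- K=8, m=1: 7/39 = 17.9% against 8/40 = 20.0%.
- K=20, m=4: 16/36 = 44.4% against 20/40 = 50.0%.

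**Step 2: bias against the true incidence.** The rule also drops ADA-positive participants with no known positive, so the net effect needs a model. Let a be the ADA-positive share and s the sub-specificity-positive share among those. Each ADA-positive participant has k ADA-positive samples, and each result is undetermined independently with probability p. Let q = (1-p)^k be the chance that all k results are determined. Assume that every sample from a sub-specificity-positive participant would test positive, and ignore the small chance that all k results are missing.

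- Truth: as.
- Literal rule: asq/(1-a+aq).
- Keep known positives and simply exclude the remaining undetermined: as/[1-a+as+a(1-s)q].

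With a=40% and s=50%, the truth is 20.0%:

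- p=2%, k=3: q=0.941; literal rule 19.3%, keep-and-exclude 20.2%.
- p=5%, k=6: q=0.735, so 26.5% of known positives are dropped; literal rule 16.4%, keep-and-exclude 21.1%.
- p=10%, k=6: q=0.531; literal rule 13.1%, keep-and-exclude 22.1%.

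With a=80%, s=25%, p=5% and k=6, the truth is again 20.0%:

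- Literal rule: 0.147/0.788 = 18.7%, low by 1.3 points.
- Keep-and-exclude: 0.200/0.841 = 23.8%, high by 3.8 points.

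At a=100% the literal rule reduces to s and has no bias. To first order in 1-q, the relative bias is -(1-q)(1-a) for the literal rule and +(1-q)a(1-s) for keep-and-exclude. The two are equal in size near a = 1/(2-s), which is about 67% at s=50% and 53% at s=10%.

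**Step 3: bounds.** Under the same model, keep known positives and count the undetermined as all negative, then as all positive:

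- a=40%, s=50%, p=5%, k=6: 20.0% to 20.0% + 20%×0.265 = 25.3%.
- a=80%, s=25%, p=5%, k=6: 20.0% to 20.0% + 60%×0.265 = 35.9%.

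The bounds contain the truth in both cases, and their width shows how much is unknown.

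**The case against.** Several objections have weight.

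- **Wording.** The IL-2 rule refers to the participants' status and could be read at participant level. The evaluability sentences could inherit the TE window from the sentence before them. The sponsor may have meant to exclude only participants without a determined positive. But the SAP does not say so, and a programmer following the text would drop known positives.
- **Size.** Every rate in the working is assumed. If missing results cluster within participants, fewer people are dropped. In the mildest random-missingness scenario the gap is 0.7 points, small beside the 90% exact interval of 10.4% to 33.2% that SAP Table 14 gives for 8/40. This stands: no particular magnitude can be claimed.
- **Direction.** A reader might infer that both reported incidences must fall below the truth. The document does not support that. Removing a known positive always lowers the proportion when K<N, but the net bias also depends on which other participants are removed. It could differ if undetermined results fall mainly on sub-specificity-negative participants.
- **Remedy.** A reader might also infer that keeping known positives and excluding the rest is always closer to the truth. Step 2 shows otherwise at high ADA incidence, and the SAP gives no expected ADA incidence.
- **Consequence.** A reader might infer that a cross-reacting participant disappears from the report. The descriptions of status over time carry no evaluability restriction, so such a result would still appear there. The secondary endpoint in Table 2 is ADA incidence against SAR444245, and no decision in the SAP rests on the two sub-specificity figures.

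**Conclusion.** The point holds as a defect in a stated derivation. As written, a participant with a determined TE-period positive for anti-PEG or IL-2 cross-reacting antibodies becomes non-evaluable if status is undetermined on another ADA-positive sample, and the window for that exclusion is not stated. Each such removal lowers the reported proportion unless all evaluable participants are positive. In a cohort of about 40, one removal can move 10.0% to 7.7% (assumed counts).

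The actual size is unknown, and it is nil if every ADA-positive sample is characterised. A net downward bias against the true incidence requires results undetermined roughly at random and some ADA-negative participants. The effect is confined to two descriptive incidences; the primary ORR and the main ADA incidence are untouched. The change is still worth making, because the rule discards known results and correcting it needs no new data.

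**What to change.** Reword both evaluability rules in section 3.7.1.2 along these lines:

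- A participant with at least one positive anti-PEG (respectively IL-2 cross-reacting) result in the TE period is evaluable and counted as positive.
- A participant is undetermined only if there is no such positive and status is undetermined on at least one ADA-positive TE-period sample.

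Report the number undetermined for each sub-specificity. Give the incidence with these participants counted all negative (ADA-population denominator) and then all positive. Do not simply exclude them: that biases the incidence upward, and at high ADA incidence by more than the present rule biases it downward.

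The cost is a change of SAP wording, one extra derivation and two bounding figures per incidence. No new samples or assays are needed.
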